#### 11 point WHO ordinal Scale[27]

- 0: Uninfected, no viral RNA detected
- 1. Asymptomatic, viral RNA detected
- 2. Symptomatic, independent
- 3. Symptomatic, assistance needed
- 4. Hospitalized, no oxygen therapy
- 5. Hospitalized, oxygen by mask or nasal prongs
- 6. Hospitalized, oxygen by non-invasive ventilation or high flow
- Intubation & Mechanical ventilation, pO2/FIO2 ≥ 150 or SpO2/FIO2 ≥ 200
- Mechanical ventilation, pO2/FIO2 < 150 (SpO2/FIO2 < 200) or vasopressors

- 9. Mechanical ventilation, pO2/FIO2 < 150 and vasopressors, dialysis or ECMO
- 10. Dead

# 6 STATISTICAL PLAN

#### 6.1 Sample Size and Power Considerations

All power calculations were performed using Stata "power" package assuming a two-tailed  $\alpha$ =0.05. The planned sample size for the trial is 50 subjects, randomized in a 1:1 ratio to anti-SARS-CoV-2 convalescent plasma versus control plasma. The primary analysis will compare the combined endpoint of mechanical ventilation or death in the anti-SARS-CoV-2 convalescent plasma and control groups.

We base our sample size projection on the ACTT-1 data [22]They reported the progression within 15 days separately for COVID-19 hospitalized requiring supplemental oxygen and those requiring high flow oxygen or non-invasive ventilation. The proportion progressing were 20% and 34%, respectively in the standard of care group and 8% and 25% in the remdesivir group progression. For our assumption we assume a 32% progression rate on the standard of care (no convalescent plasma) In the absence of treatment with convalescent plasma, we anticipate that between 10 to 30% will experience the primary outcome of mechanical ventilation or death . Using the Fisher exact test: we will reject the null hypothesis under the data scenario in the Table below.

No. Mechanical ventilation/Death (%)	Control arm (%)	Active arm (%)
	5/25 (20%)	0/25 (0%)
	6/25 (24%)	<= 1/25 (4%)
	7/25 (28%)	<= 1/25 (4%)
	8/25 (32%)	<= 1/25 (4%)
	9/25 (36%)	<= 2/25 (8%)
	10/25 (40%)	<= 3/25 (12%)

Rejection Region for the Fisher Exact Test

We will use an 8-point ordinal scale to assess clinical status, based on WHO clinical trial guidance. We assume the same distribution of outcomes for the control arm (i.e., in the absence of treatment with

convalescent plasma) as in ACTT, as tabulated below. Assuming 25 participants are treated with convalescent plasma and 25 participants are untreated, we would have 80% power to detect a difference between treatment arms as follows:

Category	Control arm (%)	Active arm (%)
Death	12%	0
Hospitalized, on invasive mechanical ventilation plus additional organ support (pressors, RRT, ECMO)	0	0
Hospitalized, intubated and mechanical ventilation	20.0%	0
Hospitalized, on non-invasive ventilation or high flow oxygen devices;	12%	8%
Hospitalized, requiring supplemental oxygen fy mask or nasal prong	0	20%
Hospitalized, not requiring supplemental oxygen – requiring ongoing medical care (COVID-19 related or otherwise);	24%	12%
Not hospitalized, limitation on activities	16%	28%
Not hospitalized, no limitations on activities.	16%	32%

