#### **Exclusion Criteria**

- 1. Contraindication to transfusion due to inability to tolerate additional fluid, such as due to decompensated congestive heart failure
- 2. Baseline requirement for oxygen supplementation prior to COVID-19 infection or use of positive pressure therapy for sleep disordered breathing
- 3. Currently experiencing severe hypoxemic failure, as defined in study endpoints
- 4. Prior receipt of plasma products, IVIG, or hyperimmune globulin within past 3 months
- 5. Not currently enrolled another interventional clinical trial of COVID-19 treatment.

Note: If taking medications with potential anti-COVID activity for the purpose of COVID-19 treatment that do not yet have data to support efficacy, such as IL-6 antagonists these medications must be stopped prior to enrollment. Receipt of current standard of care COVID-19 treatment, including remdesivir and dexmethasone is permitted and should be recorded as concomitant medications.

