#### 5.3.2 Exclusion Criteria

1. Contraindication to transfusion due to inability to tolerate additional fluid, such as due to decompensated congestive heart failure

2. Baseline requirement for oxygen supplementation prior to COVID-19 infection or use of positive pressure therapy for sleep disordered breathing

- 3. Currently experiencing severe hypoxemic failure, as defined in study endpoints
- 4. Prior receipt of plasma products, IVIG, or hyperimmune globulin within past 3 months
- 5. Currently enrolled another interventional clinical trial of COVID-19 treatment.

Note: If taking medications with potential anti-COVID activity that do not have data to support efficacy, such as IL-6 antagonists, these medications must be stopped prior to enrollment. Receipt of current standard of care COVID-19 treatment, including remdesivir is permitted and should be recorded as a concomitant medication.

Note: Pregnancy is not exclusionary but will merit additional discussion of risks & benefits in the context of ongoing pregnancy

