# 6.2 Statistical Analysis

# 6.2.1 **Primary endpoint**

Our primary hypothesis is that by providing anti-SARS-CoV-2 plasma, the rate of progression to mechanical ventilation or death will be decreased as compared to the rate in in the group receiving control plasma. We will apply a Fisher exact test to compare the combined endpoint of mechanical ventilation/death respiratory failure rates between the two groups occurring by day 15. 29. All analyses

will be conducted with a modified intention-to-treat approach, which excludes randomized subjects who do not initiate an infusion of the study plasma. As secondary analysis, we will also analyze the reduced oxygenation rate, requirement for supplemental oxygen rate, length of hospitalization, time to recovery (ordinal score 1-3) and mechanical ventilation rate, respectively, as well as occurrence of the primary endpoint by day 29 Statistical inference will be based on a two-sided Type 1 error rate of 0.05 and 95% confidence intervals.

Participants who are intubated for reasons other than hypercarbia/hypoxia, such as for a procedure or airway obstruction, will have ventilation settings evaluated to determine if need for ventilation due to hypoxia is meet. This will be determined by >12 hours of requirement for a mandatory mode of ventilation (volume control or pressure control) or Fi02 of > 40%. External adjudication of intubation for non-hypoxic/hypercarbic indication will be conducted.

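### Section 6.1 gives two conflicting control rates and no power for the primary endpoint, and three of the six boundaries in its rejection table do not reject under the planned two-sided Fisher test

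*Combined protocol and SAP*

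**What the plan says.** Section 6.1 plans 50 subjects, 25 per arm, at a two-tailed 0.05. It takes its rates from a remdesivir trial, given separately by level of oxygen support, with supplemental oxygen first and high flow (or non-invasive support) second. The figures read: "The proportion progressing were 20% and 34%, respectively in the standard of care group and 8% and 25% in the remdesivir group". It then gives the control rate twice. First: "For our assumption we assume a 32% progression rate on the standard of care (no convalescent plasma"). Then, for patients not given convalescent plasma: "we anticipate that between 10 to 30% will experience the primary outcome of mechanical ventilation or death".

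On the primary comparison it says "we will reject the null hypothesis under the data scenario in the Table below". The table lists control events against the largest number of active-arm events, each out of 25: 5 v 0, 6 v ≤1, 7 v ≤1, 8 v ≤1, 9 v ≤2, 10 v ≤3. The only power figure in the section, 80%, belongs to the 8-point ordinal scale, which is a secondary endpoint.

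Section 6.2.1 confirms the test and level: "We will apply a Fisher exact test to compare the combined endpoint" and "Statistical inference will be based on a two-sided Type 1 error rate of 0.05".

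On background treatment, Section 5.3.2 says "Receipt of current standard of care COVID-19 treatment, including remdesivir is permitted". The summary version of the exclusion criteria in Section 3 says "Receipt of current standard of care COVID-19 treatment, including remdesivir and dexmethasone is permitted", while Section 4.1.8 excludes dexamethasone given for COVID at enrolment.

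**The concern.** The two control rates describe the same arm and the same outcome, yet 32% is not inside 10–30%. A reader cannot tell which one the design rests on. The difference matters because with 25 per arm the number of control events largely decides whether the test can reject at all.

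The rejection table is the only statement in the plan of what the primary comparison can show. If its limits are too generous, the plan misstates what result would count as success and makes the design look stronger than it is. A rejection region also does not say how likely a rejection is; for that a power figure is needed, and none is given.

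Section 3 and Section 6.3 commit to recalculating the sample size if a new therapy becomes standard of care. That recalculation needs one stated starting rate.

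**Working it through.** **Inputs.** 25 per arm, two-sided 0.05, Fisher exact test (Sections 6.1 and 6.2.1). Progression rates of 20% and 34% on standard of care and 8% and 25% on remdesivir (Section 6.1). The plan gives no active-arm rate for the primary endpoint, so the active rates below are assumptions shown as a range.

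**1. The rejection table.** For 5 v 0, the two-sided p-value is 2 × C(25,5)/C(50,5) = 2 × 53,130/2,118,760 = 0.0502. The other cells follow in the same way:

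| Control events | Printed limit | p at printed limit | Rejects? | Correct limit |
|---|---|---|---|---|
| 5 | 0 | 0.0502 | no | none |
| 6 | ≤1 | 0.0983 | no | 0 (p = 0.0223) |
| 7 | ≤1 | 0.0488 | yes | ≤1 |
| 8 | ≤1 | 0.0232 | yes | ≤1 |
| 9 | ≤2 | 0.0374 | yes | ≤2 |
| 10 | ≤3 | 0.0507 | no | ≤2 (p = 0.0181) |

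A one-sided 0.05 test does not explain the printed table. It would also reject 8 v 2 (p = 0.0369) and 9 v 3 (p = 0.0477), which the table leaves out. One-sided 0.025, mid-p, chi-square with and without continuity correction, and Boschloo's test do not reproduce the whole table either.

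**2. Where 32% could come from.** Let w be the share of patients on high flow and r the remdesivir uptake, assumed equal in the two oxygen groups:

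rate(w, r) = (1 − w)(20 − 12r) + w(34 − 9r), in percent.

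- No remdesivir (r = 0): 20 + 14w = 32 gives w = 12/14 = 0.857.
- Everyone on high flow (w = 1): 34 − 9r = 32 gives r = 2/9 = 0.222.
- Full remdesivir use (r = 1): 8 + 17w, so between 8% and 25%.
- Illustration with half on high flow (an assumption): 27.0% with no remdesivir, 16.5% with all on it.

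So 32% needs at least 86% of patients on high flow even with no remdesivir, or at most 22% remdesivir uptake even with all on high flow. These bounds are extremes and do not depend on the equal-uptake assumption. The formula makes no allowance for dexamethasone.

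The 32% does match one other figure in Section 6.1: the control column of the ordinal table has 12% dead and 20% intubated, and 12 + 20 = 32.

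**3. Power of the primary comparison.** Exact power is the sum of the products of the two binomial probabilities over all outcomes with p ≤ 0.05. With no plasma events it reduces to P(Bin(25, control rate) ≥ 6). The printed region is taken as the Fisher region plus the cells 5 v 0, 6 v 1 and 10 v 3, with the correct Fisher limits beyond 10 control events; with no plasma events it gives P(Bin ≥ 5).

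| Control rate | Fisher, plasma 0% | Printed region, plasma 0% | Fisher, plasma 4% | Printed region, plasma 4% | Fisher, plasma halves the rate |
|---|---|---|---|---|---|
| 32% | 86% | 94% | 67% | 75% | 16% |
| 30% | 81% | 91% | 61% | 70% | 15% |
| 25% | 62% | 79% | 42% | 55% | 12% |
| 20% | 38% | 58% | 23% | 36% | 9% |
| 10% | 3% | 10% | 2% | 5% | 1% |

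Solving for 80% power, the plasma event rate must be about 1.5% or lower at a 32% control rate and about 0.17% or lower at 30%. With a plasma rate of exactly zero, the control rate must be at least 29.8%.

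**The case against.** **The results are sensitive to exact arm sizes.** Section 6.2.1 uses a modified intention-to-treat set that drops subjects who never start an infusion, so the analysed arms may not be 25 and 25. At 24 v 24, 5 v 0 (p = 0.0496) and 10 v 3 (p = 0.0490) reject; best-case power at a 20% control rate rises from 38% to 54%, and the 29.8% threshold falls to 26.4%. With 24 controls and 25 on plasma all three disputed cells reject. With 25 controls and 24 on plasma none does. This is correct and limits how much weight the exact percentages can bear. It does not rescue the table, which prints 25 as its denominator, and 6 v 1 still fails at 24 v 24 (p = 0.097).

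**Two of the three errors are marginal.** That is true of 5 v 0 and 10 v 3, whose p-values round to 0.05. Even so, the test does not reject there, and 6 v 1 has a p-value about twice the level.

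**The plan never claimed the power implied by its table.** Also true: that column is this review's calculation, and zero plasma events is a chosen best case. It measures the effect of the table errors and does not refute a stated power. The Fisher columns stand without it.

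**The 32% and 10–30% statements are only 2 points apart at the edge.** Going from 32% to 30% costs only about 5 points of best-case power (86% to 81%). Full remdesivir use gives 8–25%, so the source rates broadly support the range. The larger loss lies in the lower part of that range, and the plan does not mention it.

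**This is a proof-of-concept trial whose data will be pooled with others** (Sections 4.1.9 and 4.1.10). That can justify 50 patients. It does not justify an incorrect table or two conflicting assumptions.

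**Conclusion.** The concern holds. Section 6.1 gives two incompatible control rates for the same condition, states no power or active-arm rate for the primary endpoint, and prints three boundaries that the planned two-sided Fisher test does not reject at 25 per arm. One of the three is clearly wrong and two miss narrowly.

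The conclusion drawn from the trial is unaffected, since Section 6.2.1 bases inference on the test applied to the data. The harm is in planning and interpretation. At 25 per arm the smallest control count that can give a significant benefit is 6, not 5, and for nearly all of the plan's own 10–30% range 80% power is out of reach even if plasma prevents every event.

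The table errors rest only on the printed denominators, test and level. The power figures also assume 25 analysed per arm and the active-arm rates shown, and they shift noticeably if even one control patient is lost. This should be fixed, but it does not undermine the analysis.

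**What to change.** - Replace the two control-rate sentences with one rate or range. State the assumed high-flow share and the assumed background treatment: remdesivir uptake, and dexamethasone once the Section 3 criteria and Section 4.1.8 have been reconciled.
- Correct the rejection table for 25 per arm to 5: none; 6: 0; 7: ≤1; 8: ≤1; 9: ≤2; 10: ≤2.
- State the assumed active-arm rate and print exact two-sided Fisher power for n = 50 over the chosen control range. A line for slightly smaller or unequal analysed arms would show the sensitivity to the modified intention-to-treat rule.

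The cost is one rewritten paragraph, three table entries and one small power table. It needs no extra patients and no change to the analysis. The drawback is that the stated prospects of the primary comparison become less favourable.

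### Three of the six limits in the section 6.1 Fisher rejection table (5 v 0, 6 v 1 and 10 v 3 of 25) do not reject at two-sided 0.05

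*Combined protocol and SAP*

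**What the plan says.** Section 6.1 sets a two-tailed alpha of 0.05 and states: "The planned sample size for the trial is 50 subjects, randomized in a 1:1 ratio", which gives 25 per arm. It introduces its table with "Using the Fisher exact test: we will reject the null hypothesis under the data scenario in the Table below". The table gives, for each control count out of 25, the largest active count said to reject: 5 v 0, 6 v 1, 7 v 1, 8 v 1, 9 v 2 and 10 v 3.

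For the control arm, the same section takes a 32% progression rate and also says "we anticipate that between 10 to 30% will experience the primary outcome of mechanical ventilation or death". It gives no active-arm rate and no power for the primary endpoint; its 80% power statement concerns the ordinal scale.

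Section 6.2.1 specifies the same test for the analysis: "We will apply a Fisher exact test to compare the combined endpoint of mechanical ventilation/death". It adds "Statistical inference will be based on a two-sided Type 1 error rate of 0.05 and 95% confidence intervals". The analysis set is modified intention-to-treat, "which excludes randomized subjects who do not initiate an infusion of the study plasma", so the final denominators may not be 25 and 25.

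**The concern.** The table is presented as the rejection region of a fully specified test, so it can be checked exactly. Three of its six limits do not belong to that region, and all three err in the direction that makes rejection look easier.

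Two things are at stake. First, the table is the only quantitative support for 50 subjects on the primary endpoint. A reader who uses it to judge whether the trial can answer its question is given too favourable a picture, and the false entry point of 5/25 (20%) lies in the middle of the plan's 10 to 30% control range. Second, for three possible results at 25 per arm, section 6.1 says the null is rejected while the analysis in section 6.2.1 says it is not.

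**Working it through.** **Inputs.** 25 per arm, Fisher's exact test, two-sided alpha 0.05 (sections 6.1 and 6.2.1). The printed limits are those of the section 6.1 table.

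**Formula.** With c control and a active events and m = c + a, the one-sided p is the sum over k ≥ c of C(25,k)·C(25,m−k)/C(50,m). The arms are equal, so the null distribution is symmetric and the two-sided p is twice the one-sided p.

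- 5 v 0: C(25,5)/C(50,5) = 53,130/2,118,760 = 0.02508; doubled, 0.0502.
- 6 v 1: [C(25,6)·25 + C(25,7)]/C(50,7) = (4,427,500 + 480,700)/99,884,400 = 0.04914; doubled, 0.0983.
- 10 v 3: the sum over k = 10 to 13 gives 0.02534; doubled, 0.0507.

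**All printed limits.**

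| Control events | Printed active limit | Two-sided p at that limit | Rejects? | Correct limit |
|---|---|---|---|---|
| 5 | 0 | 0.0502 | no | none |
| 6 | 1 | 0.0983 | no | 0 (p=0.0223) |
| 7 | 1 | 0.0488 | yes | 1 |
| 8 | 1 | 0.0232 | yes | 1 (8 v 2: 0.0738) |
| 9 | 2 | 0.0374 | yes | 2 (9 v 3: 0.0955) |
| 10 | 3 | 0.0507 | no | 2 (p=0.0181) |

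**Does another test reproduce the printed limits 0, 1, 1, 1, 2, 3?** For 5 to 10 control events:

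- One-sided Fisher at 0.05 gives 0, 1, 1, 2, 3, 3. It admits 6 v 1 (0.0491) but also 8 v 2 (0.0369) and 9 v 3 (0.0477), which the table leaves out.
- One-sided Fisher at 0.025 gives the same limits as two-sided 0.05.
- Pearson chi-square gives 0, 1, 1, 2, 3, 3.
- Mid-p gives 0, 0, 1, 2, 2, 3.
- Boschloo and Barnard tests put 6 v 1 at 0.0505 and 0.0621.

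None of these reproduces the table. The printed percentages agree with the printed counts (1/25 = 4%, 3/25 = 12%), so the limits are not an extraction fault.

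**Size without any active-arm assumption.** With X ~ Binomial(25, control rate), no favourable rejection is possible when X ≤ 5 under the true region, or X ≤ 4 under the printed one.

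| Control rate | True, P(X ≤ 5) | Printed, P(X ≤ 4) |
|---|---|---|
| 10% | 97% | 90% |
| 20% | 62% | 42% |
| 30% | 19% | 9% |
| 32% | 14% | 6% |

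This comparison reflects 5 v 0 alone.

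**Size with assumed active rates.** The active rates are assumptions, because section 6.1 gives none for this endpoint. The chance of a favourable rejection is enumerated exactly. Printed limits replace Fisher limits for 5 to 10 control events; Fisher limits are kept elsewhere. The last three columns give each wrong cell's probability, and together they make up the gap.

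| Control v active | Printed | True | 5 v 0 | 6 v 1 | 10 v 3 |
|---|---|---|---|---|---|
| 20% v 0% | 0.58 | 0.38 | 0.196 | 0 | 0 |
| 20% v 8% | 0.19 | 0.12 | 0.024 | 0.044 | 0.002 |
| 25% v 4% | 0.55 | 0.42 | 0.059 | 0.069 | 0.003 |
| 32% v 0% | 0.94 | 0.86 | 0.080 | 0 | 0 |
| 32% v 4% | 0.75 | 0.67 | 0.029 | 0.047 | 0.007 |
| 32% v 8% | 0.52 | 0.45 | 0.010 | 0.034 | 0.021 |
| 32% v 16% | 0.19 | 0.16 | 0.001 | 0.008 | 0.023 |
| 32% v 25% | 0.049 | 0.040 | 0.000 | 0.001 | 0.007 |

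**Type I error.** With the printed limits mirrored to both directions and extended by Fisher limits outside 5 to 10 events, the maximum two-sided size over common event rates from 0.5% to 50% is 3.9% (at a 15% rate). The true Fisher region's maximum is 3.3%.

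**Dependence on denominators.**

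| Control n v active n | 5 v 0 | 6 v 1 | 10 v 3 |
|---|---|---|---|
| 24 v 25 | 0.022 | 0.049 | 0.026 |
| 25 v 24 | 0.0502 | 0.0983 | 0.0507 |
| 24 v 24 | 0.0496 | 0.097 | 0.0490 |

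All three reject in the first case, none in the second, and two of the three in the last.

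**The case against.** The arithmetic is not in dispute; the case against concerns weight.

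- Two of the three misses are at rounding level, and the largest figures come from one of them. The 62% v 42% comparison and the 20-point maximum are due wholly to 5 v 0, at p=0.0502. The one unmistakable error, 6 v 1, adds at most about 7 points in the scenarios above. This stands, and is why the gap is split by cell.
- The size depends on active rates that the plan does not give. With the control rate halved from 32% to 16% the gap is about 3 points, and at 32% v 25% it is under 1. This also stands.
- The plan states no primary-endpoint power that the error would falsify, and the computed p-value would govern in practice. That is fair, but it does not make the table correct. The plan says it will reject in these cells, and nothing else supports the sample size on this endpoint.
- A sentence saying that the p-value governs largely restates section 6.2.1. That is true of its second half. Its first half, limiting the table to 25 per arm, is new and useful, because losing one patient from an arm can change which cells reject.

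**Conclusion.** The concern holds. At 25 analysed per arm and two-sided 0.05, three of the six printed limits are wrong: 6 v 1 clearly (p=0.098), and 5 v 0 and 10 v 3 by less than 0.001. The other three are right. The lowest control count that permits a favourable rejection is 6/25 (24%).

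The p-values need no assumption beyond 25 per arm. The overstatement in the chance of rejecting rests on assumed active rates. It runs from under 1 point for small effects to about 20 points when the active rate is near zero.

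The primary analysis remains valid, since even the printed region keeps its maximum size at 3.9%. This is a should-fix correction to the sample-size justification, not a threat to the trial's conclusions.

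**What to change.** In the section 6.1 table, change three entries: for 5/25 control events, no active count rejects; for 6/25, only 0/25; for 10/25, at most 2/25. Leave the rows for 7, 8 and 9 unchanged.

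Add one sentence below it, for example: *These limits apply only to 25 analysed patients per arm; the primary conclusion rests on the two-sided Fisher p-value from section 6.2.1, computed on the final modified intention-to-treat denominators.*

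The cost is three table entries and one sentence. Test, alpha, sample size and conduct do not change. The stated region becomes less favourable, so the justification for 50 subjects should be read again against the corrected table.

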To evaluate the clinical efficacy of CCP relative to the control arm in adults hospitalized with COVID-19 according to clinical status (8-point ordinal scale) at Day 29	
 
Death;
 
Hospitalized, on invasive mechanical ventilation or ECMO;
 
Hospitalized, on non-invasive ventilation or high flow oxygen devices;
 
Hospitalized, requiring supplemental oxygen;
 
Hospitalized, not requiring supplemental oxygen - requiring ongoing medical care (COVID-19 related or otherwise);
 
Hospitalized, not requiring supplemental oxygen - no longer requires ongoing medical care;
 
Not hospitalized, limitation on activities and/or requiring home oxygen;
 
Not hospitalized, no limitations on activities.
 

OBJECTIVES	ENDPOINTS (OUTCOME MEASURES)
Additional Secondary Objectives	

 
To evaluate the clinical efficacy of different investigational therapeutics as compared to the control arm as assessed by:
 
Clinical Severity Ordinal scale:
 
Time to an improvement of one category and two categories from Day 0 (baseline) using an ordinal scale.
 
Subject clinical status using ordinal scale at Days 2,5,8,15, 29
 
Mean change in the ordinal scale from Day 1 to Days 2,5,8,15, 29
 
	
 
Clinical outcome assessed using ordinal scale daily while hospitalized and on Days 15, 29 and 120
 
Time to clinical recovery (defined as ordinal score 1-3)
 

 
National Early Warning Score (NEWS):
 
Time to discharge or to a NEWS of ≤ 2 and maintained for 24 hours, whichever occurs first.
 
Change from Day 1 to Days 2,5,8,15, 29
 
	
 
NEWS assessed daily while hospitalized
 

 
Oxygenation:
 
Oxygenation use up to Day 120.
 
Incidence and duration of new oxygen use during the study.
 
Oxygen requirement on day 1,2,5,8,15, 29
 
	
 
Days of supplemental oxygen (if applicable) up to Day 29
 
PaO2/FiO2 ratio or SpO2/FiO2
 
O2 requirement at day 120
 

 
Non-invasive ventilation/high flow oxygen:
 
Non-invasive ventilation/high flow oxygen use up to Day 29.
 
Incidence and duration of new non-invasive ventilation or high flow oxygen use during the study.
 
	
 
Days of non-invasive ventilation/high flow oxygen (if applicable) up to Day 29
 

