# 6.2.2 Secondary endpoint (clinical status):

We will evaluate the clinical efficacy of CCP relative to the control arm in adults hospitalized with COVID-19 according to clinical status (8-point WHO ordinal scale) using a proportional odds model. Because clinical status is evaluated on multiple days, we will use a generalized estimating equations (GEE) approach to account for repeated measures within each patient. Changes in ordinal scale at each timepoint will be summarized by proportions.

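### The 80% power stated in section 6.1 for the ordinal endpoint names no test or day; a two-sided single-day Wilcoxon or proportional-odds test on the printed table has about 70%.

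*Combined protocol and SAP*

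**What the plan says.** Section 6.1 states that all power calculations used Stata's power routines with a two-tailed 0.05. The Fisher exact test named there belongs to the binary primary endpoint, for which the section gives a rejection region and no power percentage. For the ordinal scale it assumes 25 treated and 25 untreated patients, takes the control distribution from ACTT, and says "we would have 80% power to detect a difference between treatment arms as follows". A table with one column per arm follows.

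Section 6.2.2 plans the analysis of this endpoint "according to clinical status (8-point WHO ordinal scale) using a proportional odds model", and adds: "Because clinical status is evaluated on multiple days, we will use a generalized estimating equations (GEE) approach". Section 6.2.1 sets the level: "Statistical inference will be based on a two-sided Type 1 error rate of 0.05 and 95% confidence intervals".

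On timing, the key secondary objective in the section 3 and section 5.1 tables assesses the arms "according to clinical status (8-point ordinal scale) at Day 29". Section 6.1 gives no day for its ordinal table. The ACTT-1 progression data cited earlier in that section are 15-day data ("They reported the progression within 15 days separately"), and from them "we assume a 32% progression rate on the standard of care".

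**The concern.** The 80% is the only power percentage in section 6.1, and it concerns the key secondary objective. The table supplies everything needed to compute power for a comparison at one time point, and the usual two-sided ordinal tests fall well short of 80% on it. Because no test or day is named, a reader cannot tell what the 80% refers to or whether it applies to the model in section 6.2.2.

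What is at stake is interpretation. A null ordinal result would be read against a 20% chance of missing the tabulated effect, when at a single time point that chance is about 30%. Section 4.1.10 also says this proof-of-concept trial is to provide preliminary data for larger trials, so an unsupported figure could be carried forward.

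**Working it through.** **Inputs (section 6.1 table; scores from the WHO scale in section 5.4).** 25 per arm, two-sided 0.05.

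| Score | State | Control % | Active % |
|---|---|---|---|
| 8 | Death | 12 | 0 |
| 7 | Ventilation plus organ support | 0 | 0 |
| 6 | Intubated, ventilated | 20 | 0 |
| 5 | Non-invasive ventilation or high flow | 12 | 8 |
| 4 | Supplemental oxygen | 0 | 20 |
| 3 | In hospital, no oxygen | 24 | 12 |
| 2 | Home, limited | 16 | 28 |
| 1 | Home, not limited | 16 | 32 |

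Both columns sum to 100%.

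**1. What reproduces 80%.** Treat the scores as a continuous measure.
- Means: 3.96 (control) and 2.44 (active), difference 1.52.
- Variances: 20.84 − 3.96² = 5.158 and 7.72 − 2.44² = 1.766, so the SDs are 2.27 and 1.33.
- Pooled SD = √[(5.158 + 1.766)/2] = 1.861, and d = 1.52/1.861 = 0.817.
- Two-sample t-test, noncentrality 0.817 × √12.5 = 2.89 on 48 df: power **80.8%** (Welch 80.4%; 81.6% by simulation for the pooled test).

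This was the only two-sided calculation tried that came within 2 points of 80%. A one-sided Wilcoxon gives 79.5%, but section 6.1 says two-tailed. A Pearson chi-square, which ignores the ordering, gives 88% (noncentral) to 94% (simulated).

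**2. Wilcoxon, single time point.** P(active better) + ½P(tie), summed over the active categories with scores 5 to 1:

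0.08×0.38 + 0.20×0.44 + 0.12×0.56 + 0.28×0.76 + 0.32×0.92 = 0.6928.

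- Noether: Φ(√(12×50×¼) × 0.1928 − 1.96) = Φ(0.401) = 65.6%.
- Noether with tie correction. The factor is 1 − Σp̄³ = 0.966, where p̄ is the mean of the two columns: Φ(√(150/0.966) × 0.1928 − 1.96) = Φ(0.442) = 67.1%.
- Simulated tie-corrected test, 400,000 trials: **69.0%** (68.6% with continuity correction). A permutation version gives 69.5%.
- The simulated test reaches 80% at about 32–33 per arm.

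**3. Proportional odds, single time point.**
- Fitting the model to the expected counts gives a log odds ratio of 1.255 (odds ratio about 3.5).
- Whitehead: Φ(1.255 × √(50×0.966/12) − 1.96) = Φ(0.559) = **71.2%**.
- Simulated likelihood-ratio test 70.8%; simulated Wald test 71.1%.

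The 3.5 is only an average. The cumulative odds ratios are infinite at the two cuts where the active arm has no events (death; ventilation or death), then 9.04, 2.02, 3.19 and 2.47. The printed columns do not follow proportional odds, so no common odds ratio should be quoted as the design effect.

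**4. The planned GEE model.** Its power depends on the distribution on each day and on the within-patient correlation. The plan gives neither, so no figure can be derived.

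**5. The day.** Control death plus ventilation is 12% + 20% = 32%. This equals the progression rate that the section assumes from 15-day data, while the objective is set at Day 29. The match is suggestive only; what is established is that section 6.1 does not say.

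**6. Sensitivity to the table (an assumption; nothing in the documents shows it).** If the control entries 0% (supplemental oxygen) and 24% (no oxygen) had been transposed in print, two-sided power would be 85.1% (Wilcoxon) and 86.9% (proportional-odds likelihood ratio). The table therefore needs confirming.

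**The case against.** The strongest reply is that nothing has been miscalculated. A two-sided t-test on the scores reproduces 80%, and the planned analysis uses repeated measures, which can add power. As an illustration outside the documents, suppose the printed distributions held on five days and each patient's mean rank were compared. Power would be about 91%, 83% or 75% at latent correlations of 0.5, 0.7 and 0.9. Smaller effects on early days would lower these figures. On this view the documents do not show that the planned analysis falls below 80%, and printing 70% would describe a test that section 6.2.2 does not plan, from a table still to be confirmed. The endpoint is also secondary, in a 50-patient trial.

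Much of this stands. The 80% may be correct for a comparison of means, so the defect is better described as an undefined figure that does not match the planned analysis than as a slip in arithmetic. The single-day 70% is not the power of the GEE model. The uncorrected Noether value of 65.6% is a poor guide with this many ties; without it the range is about 67–71%.

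It does not rescue the statement as written. A mean change in the ordinal scale is listed among the additional secondary objectives, but section 6.1 does not tie the 80% to it. For the repeated-measures model, the plan gives no assumptions from which 80% could follow.

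**Conclusion.** The concern holds. At the one pair of distributions that section 6.1 tabulates, with 25 per arm and two-sided 0.05, a Wilcoxon test has about 69% power and a proportional-odds test about 71%. The shortfall against 80% is roughly 10 percentage points: 9 to 14 over all formulas and simulations, or 9 to 13 without the uncorrected Noether value. For the GEE model in section 6.2.2 the 80% is unsupported, and its true power could lie on either side of 70%.

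The result assumes that the table is printed as intended and that one assessment per patient is compared. Which test the sponsor used is not stated, and none is attributed here. The primary analysis and the trial size are unaffected, but the figure should be corrected.

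**What to change.** In section 6.1:

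- Name the test and the day to which the two columns apply, and confirm the columns as printed.
- Once the table is confirmed, replace the 80% statement with: *about 70% power for a single-time-point proportional-odds or Wilcoxon test, two-sided 0.05*.
- Add either *power of the repeated-measures GEE model in section 6.2.2 was not calculated*, or the within-patient correlation and day-by-day distributions behind a GEE figure.
- If the 80% was meant for a comparison of mean scores, say so, and say that this is not the analysis in section 6.2.2.

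If confirmation changes the table, recompute the figure from the corrected columns.

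The cost is two or three sentences and a less favourable stated power. No analysis, error rate or sample size changes.
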